### **Safety Monitoring:**

[figure not shown]
This study will incorporate a data and safety monitoring plan with medical monitor to review study data for adverse events to ensure the safety of study subjects. Following the use of either standard treatment or TubeClear® intervention, all Subjects will receive an abdominal radiograph with contrast. Radiographs will be reviewed by a radiologist (blinded to the study) to assess for tube integrity and location, and enteral tract tissue injury that may be attributable to either intervention.

In all phases, surveillance will include assessment for adverse events related to the respective study intervention (i.e. EAD(P) displacement, EAD(P) damage, enteral tract tissue injury) and will continue for three (3) days. Patients who are discharged from the hospital prior to 3 days will be followed up by phone until completion of 3 days following study interventions. All adverse events will be reported to the IRB and medical monitor.

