- Intervention in either group is deemed successful if EAD(P) is able to be flushed with 10 ml of air within five (5) minutes following the respective intervention. The intervention is deemed unsuccessful if EAD(P) is unable to be flushed with 10 ml of air within five (5) minutes following the intervention.
- Subject will receive a portable abdominal radiograph with contrast agent following either intervention. The radiologist (blinded to the study) will assess and report the abdominal radiographs post-intervention for adverse events (i.e., EAD(P) displacement, EAD(P) damage, enteral tract tissue injury) attributable to the intervention. Study procedures carried out in IR may utilize low-dose fluoroscopy as an alternative to the portable abdominal radiograph.
- In either group, if the intervention is unable to restore EAD(P) patency, further steps to restore patency will be determined by the clinical team per usual practice.

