## **5.4 Safety Evaluation**

The FDA has deemed TubeClear® to be non-significant risk for use in this study (**Appendix D**). Following successful restoration of EAD(P), a portable abdominal radiograph with contrast agent will be obtained. A radiologist (blinded to the study) will assess the radiographs for adverse events related to the respective Intervention and report results.

Subjects will be monitored for the occurrence of adverse events defined as any untoward or unfavorable occurrence. A description of all events will be recorded in the Study database.

Anticipated adverse events (AE), or “TubeClear® Specified Events” include: EAD displacement, EAD perforation and enteral tract tissue injury.

The relationship of each event to the study protocol will be classified according to severity, expectedness and relatedness by the bedside clinicians and recorded.

Unanticipated Problems (UP) involving risk to Subjects or others will also be tracked. UP includes any incident, experience, or outcome that is unexpected, related or possibly related to Intervention, and suggests that research places Subjects or others at greater risk for harm.

An AE is a reportable Serious Adverse Event (SAE) if it is serious, unexpected and related or possibly related to the Intervention.

**Expedited** reporting timeline for all SAE and unanticipated problems related to the Intervention or from protocol violations:

- a. Principal Investigator or designee will notify their local IRB, medical monitor and AMI **within 24 hours of the event.**

A full narrative report describing the event within 7 calendar days will be submitted to the local IRB, medical monitor and AMI. Such reports will include a detailed description of the SAE/UP, an explanation of the basis for determining that the event represents a SAE/UP, and a description of any corrective actions that are proposed in response to the SAE/UP.

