#### **6.3.4 Secondary Objective Analysis**

Data from Phase I and Phase IIA will be observational and will not test a hypothesis. Data on 1) pain, using established age-appropriate pain scales, 2) physiologic changes in vital signs, 3) distress related EAD(P) events, and 4) adverse events related to TubeClear® use will be described and reported as counts and percentages.

In Phase IIB, the secondary objectives between TubeClear® intervention and CHOP Standard Treatment include comparison of 1) time to intervention, 2) pain using established age-appropriate pain scales, 3) physiologic changes in vital signs, 4) distress related EAD(P) events, and 5) adverse events related to either group.

1. A log-rank test will be performed to compare intervention time of TubeClear® intervention to the CHOP Standard Treatment.
2. A Wilcoxon rank sum test will be performed to compare differences in subject pain and discomfort between TubeClear® intervention and CHOP Standard Treatment.
3. A t-test will be performed if the distributions are normal (or non-parametric equivalent, if the distributions are not normal) to compare differences in physiologic changes (i.e. vital sign changes) between TubeClear® intervention and CHOP Standard Treatment.
4. A Wilcoxon rank sum test will be performed to compare differences in distress related EAD(P) events (i.e. subject behavior such as pulling/yanking) between TubeClear® intervention and CHOP Standard Treatment.
5. A chi-square analysis (or Fisher's exact test) will be performed to compare the proportions of adverse events (i.e., EAD(P) displacement from the intervention; EAD(P) damage from the intervention; any enteral tract tissue perforation from the intervention) in TubeClear® intervention and CHOP Standard Treatment.

Intention-to-treat analysis will be used to compare the secondary endpoints between the TubeClear® intervention and the CHOP Standard Treatment. Patients will be analyzed according to their randomized allocation. Full reporting of any deviations from random allocation and missing responses will be recorded and assessed in accordance with the CONSORT guidelines. Exploratory-per-protocol analysis will also be reported.

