#### **9.1.2 Blinding**

This Study will be blinded to the radiologist reading the abdominal radiographs post-intervention. The Study will not be blinded to the Investigators, Study Nurse, or other research staff due to the nature of the interventions in this Study.

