### **9.4 Regulatory and Ethical Considerations**

#### **9.4.1 Data and Safety Monitoring Plan**

This study will incorporate a data and safety monitoring plan with a medical monitor to ensure adequate human subject protection. The medical monitor (TBD) will review study data monthly for adverse events to ensure the safety of study subjects. The medical monitor will be a physician knowledgeable in pediatric critical illness and unrelated to the study. The study PI will be notified of all serious adverse events within 24 hours of knowledge of event. Notification will be by any member of the study staff who is made aware of a serious adverse event. Study data are collected daily by the research personnel, and therefore review for SAE/AE's occurs daily while patients are actively on the study protocol. Identification of an SAE will prompt chart review by the site PI to determine possible relatedness to the study protocol. Should study subjects have serious adverse events related to study interventions, the PI will report these to the IRB, the Medical Monitor, and AMI to determine continuation of the study protocol within 24 hours of being notified of an SAE.

Oversight for the conduct of the Study will be provided by the Investigators. Adverse events are not anticipated, but any occurring will be documented and reported according to IRB policies and procedures. Study personnel will be solely responsible for data collection and verification. Confidentiality will be protected by utilizing a code number as the only identifier for each Subject and the master list (i.e., Enrollment Form) will be kept secured with access limited to the immediate Study team only.

- Investigators are responsible for oversight in conducting the Study.
- Study Sponsor will conduct monthly monitoring of the Study to verify that the protocol is being followed, data collected accurately, and reports filed as required.

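### The Phase IIB adverse-event comparison counts only events attributed to the intervention, and the plan does not say whose attribution decides

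*Combined protocol and SAP*

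**What the plan says.** Four parts of the protocol bear on which adverse events are counted in Phase IIB.

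- **The radiograph read.** Section 4.2 (Phase IIB overview): "The radiologist (blinded to the study) will assess and report the abdominal radiographs post-intervention for adverse events". The events sought are "i.e., EAD(P) displacement, EAD(P) damage, enteral tract tissue injury) attributable to the intervention". Section 3.1.2 sets the same task. Sections 2.2 and 6.2 refer to either intervention, and the abstract's safety paragraph is softer still: "enteral tract tissue injury that may be attributable to either intervention".
- **Blinding.** Section 9.1.2: "This Study will be blinded to the radiologist reading the abdominal radiographs post-intervention". It continues: "The Study will not be blinded to the Investigators, Study Nurse, or other research staff". No one else is described as blinded.
- **Relatedness.** Under section 5.4 each event is "classified according to severity, expectedness and relatedness by the bedside clinicians and recorded". For serious events section 9.4.1 adds: "Identification of an SAE will prompt chart review by the site PI to determine possible relatedness to the study protocol".
- **The comparison.** Section 6.3.4 item 5 compares the arms by chi-square or Fisher's exact test on "EAD(P) displacement from the intervention; EAD(P) damage from the intervention; any enteral tract tissue perforation from the intervention".

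**The concern.** The tested endpoint is not all events but events judged to come from the treatment, so someone must make that judgement before an event is counted. The plan names two possible sources, the blinded radiologist and the bedside clinicians. It does not say which governs item 5 or how a disagreement is settled.

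Attribution could plausibly differ by arm. Section 5.4 labels displacement, perforation of the tube and tissue injury as events specific to the device, and section 8.1 lists puncture and tube damage as harms of the Clearing Stem. Both invite attribution in the device arm. Sections 8.1, 9.4.1 and 9.5.3 say that adverse events are not anticipated, which invites the opposite. The bias could therefore run either way.

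At stake is the trial's only randomised comparison of adverse events. Section 9.5 says the data may be used in an FDA premarket notification.

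**Working it through.** **1. The plan's own figure.** The only Phase IIB sample size is 17 per group (section 6.4), set for efficacy with 95% against 50% success, alpha 0.05 and power of at least 0.80. Full enumeration of the two-sided Fisher test gives power of 77.7% at 16 per group and 81.3% at 17, so the figure reproduces. No sample size or event rate is given for the adverse-event comparison.

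**2. The sections side by side.**

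| Step | Who | Knows the arm? | Attribution asked for? |
|---|---|---|---|
| Pre-intervention film (4.2) | Investigator | Not blinded (9.1.2) | No; notes pre-existing damage |
| Post-intervention film (3.1.2, 4.2) | Radiologist | Blinded | Yes |
| Relatedness of each event (5.4) | Bedside clinicians | Not named in 9.1.2; very likely yes | Yes |
| Relatedness of serious events (9.4.1) | Site PI | Not blinded | Yes |
| Counting for the test (6.3.4 item 5) | Not stated | Not stated | Yes, built into the endpoint |

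That bedside clinicians know the arm is an inference. Only the radiologist is blinded, and section 3.3.1 estimates about 30 minutes for one treatment and four hours for the other. No text gives the earlier film to the radiologist.

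**3. Event definitions.** The radiologist looks for enteral tract tissue injury, while item 5 counts tissue perforation. A non-perforating injury seen on the blinded read has no stated place in the comparison.

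**4. Illustration of size (assumed rates).** Let the true finding rate q be the same in both arms, and let aT and aC be the proportions attributed in the device and control arms. The spurious risk difference is q × (aT − aC). The rejection probability is the sum, over all pairs of counts out of 17, of Binomial(17, q·aT) × Binomial(17, q·aC) wherever the two-sided Fisher p is at most 0.05.

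| q | All attributed in both arms: rejection | 90% v 60%: difference, rejection | 90% v 30%: difference, rejection |
|---|---|---|---|
| 5% | 0.1% | 1.5 points, 0.05% | 3 points, 0.06% |
| 10% | 0.8% | 3 points, 0.6% | 6 points, 0.9% |
| 20% | 1.9% | 6 points, 2.8% | 12 points, 7.1% |
| 30% | 2.0% | 9 points, 4.4% | 18 points, 15.8% |

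For example, at q = 20% with 90% v 30%: 0.20 × (0.90 − 0.30) = 0.12. Exchanging the arms reverses the sign and leaves the rejection probability unchanged.

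**5. What moves the p-value.** With k events in one arm and none in the other, two-sided Fisher p = 2 × C(17,k) / C(34,k).

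- k = 2: 2 × 136 / 561 = 0.48
- k = 3: 2 × 680 / 5,984 = 0.23
- k = 4: 2 × 2,380 / 46,376 = 0.10
- k = 5: 2 × 6,188 / 278,256 = 0.044

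Against zero events, at least five are needed for significance. At low event rates, differential attribution distorts the reported proportions more than the test result.

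**The case against.** A reader might infer four stronger things. The documents do not support them.

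- **That a blinded reader cannot judge attribution at all.** The wording about either intervention in sections 2.2 and 6.2, and the softer abstract, let a reader blinded to arm report findings compatible with a clearing procedure. Only an arm-specific causal call is out of reach.
- **That the comparison rests on attribution by unblinded bedside staff.** Section 6.3.4 names no source. Section 5.4 places the bedside classification in a passage that leads into expedited reporting, and the radiologist's report can equally be read as the source for radiographic events. The text permits the unblinded route but does not prescribe it.
- **That the blinded safeguard is lost.** Section 5.4 records a description of all events, section 8.1 defines adverse events regardless of relatedness, and section 9.4.1 has a medical monitor unrelated to the study review the data monthly. An event judged unrelated is still recorded, so a comparison regardless of attribution remains possible.
- **That one or two reclassifications would decide the result.** With two to four events against none, p runs from 0.48 to 0.10, so moving between those counts does not cross 0.05. Only near a split such as five against none could a single event do so.

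It is also fair to say that this is the fifth-listed secondary comparison and has no stated power. What stands after all this is that the planned comparison has an attribution filter, that no one is named to apply it, and that the sections name different events.

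**Conclusion.** The concern holds as a gap in the endpoint definition. Item 5 restricts the comparison to attributed events and leaves open whether the blinded report or the bedside classification decides. This allows arm-dependent attribution to bias the result in either direction.

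The size cannot be derived from the documents. The 3 to 18 points above rest on assumed finding rates of 5% to 30% and a wide attribution gap (90% v 30%); with 90% v 60% the range is 1.5 to 9 points. The chance of a falsely significant test stays below 5% except with the wide gap at finding rates of 20% or more. The mismatch between tissue injury and tissue perforation is a separate inconsistency to reconcile. The primary efficacy analysis and the 17 per arm are untouched.

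**What to change.** 1. **Sections 3.1.2 and 4.2 (Phase IIB).** Remove the causal qualifier from the radiologist's task. The blinded read records displacement, tube damage and tissue injury as present or absent. Where an earlier film is available, it is supplied to the radiologist and each finding is also classed as new, pre-existing or indeterminate.
2. **Section 6.3.4 item 5.** Make the main comparison all such events by randomised arm regardless of attribution. It should cover the blinded read plus events recorded during the three-day surveillance, so that later events and those reported by phone are not dropped. Report events judged related as a supportive analysis, naming who makes that judgement.
3. **Event terms.** Reconcile tissue injury in section 4.2 with tissue perforation in section 6.3.4, so that the read and the test use one definition.

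The cost is wording and a short read form; the reader, the post-intervention imaging and the test are already planned. There are two downsides. Some incidental events unrelated to treatment will be counted in both arms. Calling a finding new is also less certain when the earlier film is old or without contrast: section 4.2 requires only the most recent film, and section 5.1.6 mentions contrast only for the post-intervention one. The indeterminate category is there for that case.

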#### **4.3 Follow-up Phase**

Follow-up surveillance will include assessment for any adverse event(s) related to the intervention (i.e. EAD(P) displacement, EAD(P) damage, enteral tract tissue injury) and will continue for up to three (3) days following interventions in all study phases regardless of study intervention allocation. Clinical Assessment Measurements (i.e., pain, feeding tolerance, and usual measures to determine EAD(P) location) will be performed prior to, immediately following, and for up to three days after the intervention. Patients who are discharged from the hospital prior to three days will be followed up daily by phone for Clinical Assessment Measurements i.e., pain, feeding tolerance and EAD(P) location as assessed by caregiver until post Intervention day three.

#### **4.4 Unscheduled Visits**

There are no anticipated unscheduled visits in this Study.

#### **4.5 Concomitant Medication**

All prior and concomitant medications used within 1 day prior to the Subject's Study Intervention procedure and through the end of the Study Intervention will be recorded. The total doses of medications administered throughout this time will be included.

#### **4.6    Rescue Medication Administration**

There are no Rescue Medications administered in this Study.

#### **4.7    Subject Completion/Withdrawal**

Subjects may withdraw from the Study at any time without any change in their clinical management for any reason that the Subject, parent(s) or guardian(s) provide. They may also be discontinued from the Study at the discretion of the Principal Investigator if any significant Adverse Events (AEs) occur, or if the attending physician requests discontinuing a Subject if there is a perceived interference with a planned procedure. The Principal Investigator or the Study Sponsor may also withdraw Subjects who are not compliant with the Study plan, or to protect the Subject for reasons of safety or for administrative reasons. It will be documented whether or not each Subject completes the clinical Study. If the Principal Investigator becomes aware of any serious, related adverse events after the Subject completes or withdraws from the Study, they will be recorded in the source documents as well as on the Case Report Forms (CRF) with appropriate notification to the IRB.

##### **4.7.1    Early Termination Study Visit**

Subjects who withdraw from the Study will receive care according to CHOP standard procedures without any change to their clinical care. Adverse events from Study Intervention will be assessed for up to three (3) days following Intervention or until patient discharge (whichever is earlier). Patients who are discharged from the hospital prior to three days will be followed up daily by phone for Clinical Assessment Measurements (i.e., pain, and feeding tolerance) until post Intervention day 3.

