In Phase IIB, Subject pain will be assessed before and after use of either intervention using established age-appropriate pain scales. Acute changes in physiologic parameters will be measured, including changes in heart rate, blood pressure and respiratory rate. Distress related EAD(P) events which may be manifested by pulling or yanking of the EAD(P) will be monitored in relation to either intervention. Following either intervention, each Subject will receive an abdominal radiograph with contrast. Radiographs will be reviewed by a radiologist (blinded to the study) for EAD(P) adverse events (i.e., EAD(P) displacement, EAD(P) damage, enteral tract tissue injury) attributable to either intervention. Incidence of adverse events attributable to the intervention (i.e. EAD displacement, EAD damage, enteral tract tissue injury) following the intervention will be monitored and reported in both groups.

In all phases, surveillance will include daily assessment for adverse events related to the respective study intervention (i.e. subject pain, feeding intolerance, EAD(P) displacement, EAD(P) damage, enteral tract tissue injury) and will continue for three (3) days. Patients who are discharged from the hospital prior to 3 days will be followed up daily by phone until completion of 3 days following study interventions.

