## 5 STUDY EVALUATIONS AND MEASUREMENTS

### 5.1 Screening and Monitoring Evaluations and Measurements

#### 5.1.1 Medical Record Review

Information from the medical record will be recorded and used for this study. This information will include medical history, information about your condition, lab and radiology results, medications, treatments, vital signs, and the response to treatments. We will be reviewing the medical record throughout the study.

We plan to follow-up all subjects for 3 days post-intervention in all study phases. It is possible that some study subjects might be discharged from the hospital prior to this endpoint. In such instances, we will need to contact the parent/guardian of the subject (as third party and not part of research procedures) and administer the follow-up questionnaire on a daily basis (till post-intervention day 3). As we cannot predict which subject is likely to be discharged prior to 3 days, we will obtain contact information for parents/guardians of all subjects at the time of obtaining informed consent.

Variables that will be abstracted from the EHR will include the following.

- Basic demographic information including subject name, medical record number (MRN), account number (CSN), Date of birth (DOB), race, ethnicity, sex, age at time of Study Intervention, weight, stature, calculated BMI, location (PICU/PCU/IR) and dates of hospitalization (length of stay)
- Contact information of parent/guardian will be collected to follow-up subjects for study related events, (in case subject is discharged prior to post-intervention day 3)
- Type of EAD(P)
- Date and place of EAD(P) insertion
- Length of EAD(P)
- EAD clog information
- Medications
- Nutrition
- Diagnoses
- Procedures
- Severity of illness
- Ventilator parameters (if applicable)
- Medications administered through EAD(P) preceding clog

- Nutrition administered through EAD(P) preceding clog
- Past Medical History
- Past Surgical History
- Established age-appropriate pain scales
- Laboratory results and radiology results

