### **6.3.6 Safety Analysis**

All Subjects entering the Study will be included in the safety analysis. Clinical Patient Assessment Measurements (i.e., pain, feeding tolerance, and usual measures to determine EAD(P) location) will be performed prior to, immediately following, and for up to three (3) days after all Interventions. Clinically significant changes will be addressed and managed by the Subject's medical team, but recorded, reported, and followed by the Study team. Surveillance will include assessment for any adverse event(s) related to the intervention (i.e. EAD(P) displacement, EAD(P) damage, enteral tract tissue injury) and will continue for up to three (3) days following interventions in either group. Patients who are discharged from the hospital prior to three days will be followed up daily by phone for Clinical Assessment Measurements i.e., pain, feeding tolerance and EAD(P) location as assessed by caregiver until post intervention day three.

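### Section 4.7.1 ends adverse-event assessment at discharge for withdrawn subjects who leave before day 3 and omits tube location from their calls, contradicting the rest of the protocol

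*Combined protocol and SAP*

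**What the plan says.** Section 4.7.1 covers subjects who leave the study early. Of their safety follow-up it says: "Adverse events from Study Intervention will be assessed for up to three (3) days following Intervention or until patient discharge (whichever is earlier"). The next sentence has those discharged before three days "followed up daily by phone for Clinical Assessment Measurements (i.e., pain, and feeding tolerance) until post Intervention day 3".

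Section 4.7 sets out how a subject comes to leave. One route is a safety decision: "They may also be discontinued from the Study at the discretion of the Principal Investigator if any significant Adverse Events (AEs) occur". It also lets the investigator or sponsor withdraw a subject on safety grounds. Events after completion or withdrawal are recorded if they are serious and related and the investigator becomes aware of them.

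The general follow-up text differs. Section 5.1.1 states: "We plan to follow-up all subjects for 3 days post-intervention in all study phases". The Abstract (Safety Monitoring) says that patients discharged early "will be followed up by phone until completion of 3 days following study interventions". Section 2.2, repeated in 6.2, describes daily surveillance for adverse events ("i.e. subject pain, feeding intolerance, EAD(P) displacement, EAD(P) damage, enteral tract tissue injury) and will continue for three (3) days"). Section 4.3 gives the content of the calls as "pain, feeding tolerance and EAD(P) location as assessed by caregiver until post Intervention day three", and 6.3.6 has discharged patients "followed up daily by phone for Clinical Assessment Measurements i.e., pain, feeding tolerance and EAD(P) location as assessed by caregiver until post intervention day three". Section 6.3.6 also puts all subjects who enter the study into the safety analysis.

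**The concern.** Section 4.7.1 is the only section on early termination, so it is the text that site staff would follow when a child is withdrawn. It sets a different end of adverse-event assessment and a shorter list of call questions from those used everywhere else, and gives no reason for either.

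The missing question matters because displacement is one of the three EAD(P) adverse events in the list of definitions, and section 6.3.4 compares it between the Phase IIB arms. After discharge, the caregiver's report of tube location is the planned way to learn of it. A withdrawn child who goes home before day 3 would stay in the safety denominator without being asked. Some of these children may have been removed because of a safety concern, and incomplete follow-up is least welcome there. In Phase I, the adverse-event summary for 15 subjects also informs the IRB's decision to continue (sections 3.1 and 6.5).

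**Working it through.** The protocol states no figure on this point, so the check compares the texts.

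**Length of adverse-event assessment**

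| Source | Who | Ends |
|---|---|---|
| Abstract, 2.2, 6.2 | all phases | three days, with phone contact after early discharge |
| 5.1.1 | all subjects | three days, with daily phone contact after early discharge |
| 3.1.3, 3.3.1, 4.3, 6.3.6 | all phases or groups | up to three days |
| 4.7.1 | withdrawn subjects | three days or discharge, whichever comes first |

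**Content of the phone call after early discharge**

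| Source | Pain | Feeding tolerance | Tube location |
|---|---|---|---|
| 3.1.3, 3.3.1, 4.3, 5.1.6, 6.3.6 | yes | yes | yes |
| 4.7.1 | yes | yes | no |

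Follow-up by group is then:

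1. Not withdrawn: surveillance for three days. If discharged early, daily calls to day 3 that include tube location.
2. Withdrawn and still in hospital on day 3: assessment to day 3, the same length as group 1.
3. Withdrawn and discharged before day 3: stated adverse-event assessment ends at discharge. Calls run to day 3 without the location question.

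Only group 3 is affected. Three other provisions might close the gap:

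- Section 4.7 captures later events only if they are serious and related and come to the investigator's notice. A non-serious displacement does not qualify.
- Section 9.4.1 provides daily review while patients are actively on the protocol, which plausibly leaves out withdrawn subjects.
- The post-intervention radiograph (3.1.2, 4.2) is a single time point and cannot show a later displacement.

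None of them reliably picks up a non-serious displacement after discharge. The size of group 3 would need a withdrawal rate and an early-discharge rate. The documents give neither.

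**The case against.** Much can fairly be said for the existing text. Calls under 4.7.1 run to day 3, so the length of contact is the same as for everyone else. Sections 2.2 and 6.2 list pain and feeding intolerance as adverse events, so part of adverse-event surveillance continues after discharge. Section 5.1.1 promises a daily questionnaire for all subjects, and although its items are not listed it may ask about the tube. Adverse events are not a separate call item in 4.3 or 6.3.6 either. In listed call content, tube location is the only difference.

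A reader might go further and infer any of the following. The documents do not support them.

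- *Children discontinued for an adverse event get the shortest follow-up.* The rule applies to all withdrawals, bites only on discharge before day 3, and leaves the length of phone contact unchanged. Section 4.7.1 speaks of subjects who withdraw, while the adverse-event clause in 4.7 speaks of discontinuation. That 4.7.1 covers safety removals is a reasonable reading, helped by 4.7's use of withdrawal for safety grounds, but it is not stated.
- *Discharge on day 0, 1 or 2 loses all, two thirds or one third of surveillance.* This counts the day-3 calls as nothing.
- *Device-event rates are biased downward.* The event that prompted removal is already recorded and counts in the proportions compared under 6.3.4. Only a further or evolving event could be missed.
- *A child treated in IR and sent home the same day has almost no assessment.* The documents give no discharge timing, and a contrast radiograph, or fluoroscopy in IR, is planned after the intervention, although 5.4 words it as following successful restoration.

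What survives is the contradiction itself. A discharge cut-off appears in one section only, and the question that would reveal a displaced tube is missing from the same section.

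**Conclusion.** Wrong as written: an internal contradiction. For withdrawn subjects discharged before day 3, section 4.7.1 ends adverse-event assessment at discharge and drops tube location from the calls. The rest of the protocol provides three days of follow-up with location asked, and 6.3.6 counts these subjects in the safety analysis. If 4.7.1 is followed, a later non-serious displacement could go unrecorded.

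The size is unknown and the group could be empty. For scale, one event is 1/15 = 6.7 percentage points in Phase I or IIA and 1/17 = 5.9 points in a Phase IIB arm. That is true of any single event in this trial and says nothing about how likely one is to be missed.

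The conclusion assumes that staff would apply 4.7.1 as written to withdrawn subjects. That it reaches children removed for safety reasons rests on reading 4.7 and 4.7.1 together.

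**What to change.** Reconcile section 4.7.1 with the rest of the protocol through two wording changes:

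1. Delete the clause that lets discharge end adverse-event assessment, so that the period is three days after the intervention.
2. Add caregiver-assessed EAD(P) location to the daily calls, matching sections 4.3 and 6.3.6.

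Apply both to any subject who received an intervention, unless consent for contact is withdrawn.

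The cost is one more question per call. Section 4.7.1 already schedules the calls to day 3, and section 5.1.1 already collects contact details for all subjects at consent.
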